***MEDICAL UNIVERSITY OF SOUTH CAROLINA***

**Study Protocol**

**Study Title: The SPARC App: A Smartphone Application for the Management of Sarcoidosis-Associated Fatigue**

**PI: Dr. [name]**

**Date and Version of Protocol:**  
V6, 9/21/21

|                             |  |
|-----------------------------|--|
| Title                | The SPARC App: A Smartphone Application for the Management of Sarcoidosis-Associated Fatigue   |
| Clinical Phase       |  |
| Objective            | To develop, refine, and test a smartphone app intended to decrease fatigue in sarcoidosis patients   |
| Endpoints            | Primary 
 
• Feasibility and usability
 
 Secondary 
 
• Changes in SAF, self-efficacy, stress, autonomous motivation, and QoL.
 
   |
| Study Population     | Sarcoidosis patients with significant sarcoidosis associated fatigue   |
| Number of Subjects   | 50   |
| Number of sites      | 1  |
| Study Duration       | 12 months  |
| Study Design         | Conduct a 12 week, 2-arm (SPARC vs. enhanced Standard Care) feasibility RCT in 50 SPs with SAF. Evaluations will occur at baseline, weeks 4 & 12 and a post-trial follow-up at week 24. The SPARC App will include stress and fatigue management tools previously developed using subject input. Standard of care includes education on stress and fatigue in addition to offering referral to outpatient pulmonary rehab. 
2a: Primary outcomes of feasibility benchmarks: <math>\geq 80\%</math> recruitment, <math>\geq 80\%</math> retention rates & usability; <math>\geq .70</math> adherence to twice daily BAM sessions; <math>\geq 75\%</math> of sample will score above average on usability & satisfaction questionnaires (SUS <math>>68</math>, uMARS <math>>64</math> & TSUQ <math>>60</math>).
 
2b: Secondary outcomes of changes in SAF, self-efficacy, stress, autonomous motivation, and QoL.
 |
| Assessments          | 
 
• Feasibility and usability: <math>\geq 80\%</math> recruitment, <math>\geq 80\%</math> retention rates & usability; <math>\geq .70</math> adherence to twice daily BAM sessions; <math>\geq 75\%</math> of sample will score above average on usability & satisfaction questionnaires (SUS <math>>68</math>, uMARS <math>>64</math> & TSUQ <math>>60</math>).
 
• Efficacy (exploratory): Changes in SAF, self-efficacy, stress, autonomous motivation, and QoL.
 
  |
| Statistical Analyses | Data will be summarized descriptively for all measures and variables. Analysis of feasibility and usability measures, as well as preliminary efficacy measures will be described in detail in additional sections included in this protocol  |

## SCHEDULE OF ASSESSMENTS

Table 1: Schedule of Assessments

| Trial Week                       |  | Clinical Trial Period |   |    | Follow-up |
|----------------------------------|--|-----------------------|---|----|-----------|
|                                  |  | 0
(Screening)      | 4 | 12 | 24        |
|                                  | Demographics a                                  | X                     |   |    |           |
|                                  | Weight   | X                     |   | X  |           |
|                                  | Height   | X                     |   |    |           |
|                                  | Medical History  | X                     |   |    |           |
|                                  | Concomitant Medications                                    | X                     | X | X  | X         |
|                                  | Eligibility Review   | X                     |   |    |           |
|                                  | Percent Recruitment and Drop-out Rate                      |                       |   | X  |           |
|                                  | System Usability Scale (SUS)                               |                       |   | X  |           |
|                                  |  |                       |   |    |           |
| Feasibility and System Usability | uMARS b   |                       |   | X  |           |
|                                  | TSUQ c  |                       |   | X  |           |
|                                  | Adherence d                                     |                       |   | X  |           |
|                                  | FSE e   | X                     |   | X  |           |
|                                  | TSRQ f  | X                     |   | X  |           |
| SDT Constructs                   | VBG g   | X                     |   | X  |           |
|                                  | Fatigue Assessment Scale (FAS) h                | X                     | X | X  | X         |
|                                  | King's Sarcoidosis Health Questionnaire (KSQ) i | X                     | X | X  | X         |
| Exploratory Outcomes             | Perceived Stress Scale (PSS) j                  | X                     | X | X  | X         |
|                                  | International Physical Activity Questionnaire k | X                     | X | X  | X         |

a Age, sex, race, income, education level, employmentb User Version of Mobile App Rating Scale (uMARS;  $\alpha = .90$ , test-retest [2,3 mos] .66, .70)c Patient/Provider SPARC Treatment Satisfaction & Usability Scale (TSUQ;  $\alpha = .82-.96$ , test- retest [1wk] .98)d % adherence to SPARC meditation dose(10min BID for 12 weeks)e Fatigue Self-Efficacy Scale (FSE;  $\alpha = 0.89-0.94$ )f 94 Autonomous Self-Motivation (TSRQ;  $\alpha = .81- .84$ )g 80, Values, Beliefs, Goals Questionnaire (VBG;  $\alpha = .72-.93$ ; Test-retest (2 week) .52-.89)h Fatigue Assessment Scale (FAS;10 items,  $\alpha = 0.8-0.89$ ; Test-retest 0.89)i King's Sarcoidosis Health Questionnaire (KSQ)j Stress (PSS-10 items;  $\alpha = 0.78$ )k International Physical Activity Questionnaire: (test-retest (8-10days) .8)

## LIST OF ABBREVIATIONS

| Abbreviation | Definition  |
|--------------|---|
| SAF          | Sarcoidosis Associated Fatigue                        |
| BAM          | Breathing Awareness Meditation                        |
| TT           | Tension Tamer   |
| SPARC        | Sarcoidosis Patient Assessment and Resource Companion |
| RCT          | Randomized Control Trial                              |
| SP           | Sarcoidosis Patients                                  |
| SC           | Standard of Care                                      |
| QOL          | Quality of life                                       |
| PSS          | Perceived stress scale                                |

## 6 INTRODUCTION

### Overview of Sarcoidosis and Sarcoidosis associated fatigue

Sarcoidosis is a systemic granulomatous inflammatory disease that disproportionately impacts African Americans. Sarcoidosis associated fatigue (SAF) is the most commonly reported symptom (80%) and considered the most important predictor of quality of life (QoL) due to its negative effects on physical and psychological health. Pharmacologic therapy for SAF is unreliable, and while several formal group-based exercise/rehabilitation programs conducted in Europe have been efficacious in reducing SAF, dissemination of such programs is limited by availability and costs in an American sarcoidosis population with high poverty rates and reduced healthcare access. Strong associations (r range: 0.54 to 0.89) have been observed between SAF and stress levels, stress-induced negative affective states (anxiety, depression) and reduced QoL. Stress levels and associated negative affective states have been managed in other chronic diseases characterized by high fatigue (e.g., cancer, HIV, COPD) using cognitive behavioral stress management tactics, including various types of relaxation exercise such as breathing meditation.

Mobile health technology-based (mHealth) solutions are increasingly being used to help patients improve healthcare knowledge, increase health-promoting behaviors and adherence to medical regimens. Our work and that of others using theory based, patient/provider guided iterative design have found high patient receptivity to mHealth self-management programs. To date, no mHealth apps have been developed to assist sarcoidosis patients (SPs) in managing SAF.

## 7 STUDY OBJECTIVE

The objective of this proposal is to conduct a randomized control trial evaluating the Sarcoidosis Patient Assessment and Resource Companion (SPARC) App, including assessing the feasibility of our study methodology, and estimating variability of outcomes and treatment effect on stress and fatigue and QOL measures. We hypothesize the SPARC App will be deemed a feasible, acceptable tool with high usability among sarcoidosis patients. Additionally, we expect to experience preliminary signals of clinical efficacy and obtain estimates of variability of changes in secondary outcomes such as perceived stress, fatigue, quality of life and self-efficacy due to engagement in the SPARCs breathing awareness meditation module.

Specific aims of this proposal are:

Specific Aim 1. Conduct a 12 week feasibility RCT with a follow-up at 24 weeks with 50 SPs with SAF. They will be randomly assigned to SPARC or an enhanced attention control group stratified by healthcare provider. They will be evaluated at baseline, 4, 12 and 24 weeks.

2a. Demonstrate feasibility of SPARC (benchmarks:  $\geq 80\%$  recruitment,  $\geq 80\%$  retention rates) and usability ( $\geq .70$  adherence to twice daily SPARC sessions); usability and treatment satisfaction scores:  $\geq 75\%$  will score above average on usability & satisfaction questionnaires (SUS  $>68$ , uMARS  $>64$  & TSUQ  $>60$ ). Back-end analytics will assess uptake of SPARC App (total engagement time) and its features (e.g., frequency of provider service line use, FAQ, video clips- sarcoidosis, fatigue & stress educational modules, sarcoidosis patient testimonials, etc.).

2b. Obtain estimates of variability of changes in secondary outcomes: stress (PSS), SAF,

QoL, fatigue self-efficacy (FSE) & autonomous motivation (TSRQ).

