### 9.1.2 Screening

All SPs will be recruited at MUSC's Sarcoidosis Clinic. In the last year 924 unique sarcoidosis patients were seen at the clinic (over 2,000 patient encounters). [name] is present in clinic 5 days/week, and sees a relatively high number of new sarcoidosis patients each week (20% of scheduled sarcoidosis patients). All sarcoidosis patients seen at MUSC complete the Fatigue Associated with Sarcoidosis (FAS) scale as part of their standard of care. Sarcoidosis patients with "significant" fatigue, defined by a FAS score  $\geq 22$ , will be offered the opportunity for screening to participate in the trial (see Inclusion and Exclusion criteria below). Screening for eligibility for participation in the trial will be conducted via a combination of chart review and direct self-report from patients on defined inclusion and exclusion criteria, outlined below. Based on the demographics of MUSC's sarcoidosis patient population, we estimate enrolled subjects will be 65% African American and 63% female.

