## SPARC

treatment satisfaction ( $\geq 75\%$  of sample will score above average on SUS(>68), uMARS (>64), TSUQ (>60)).

**Secondary outcomes:** Differences between the SPARC & SC groups in changes in fatigue (SAF), fatigue self-efficacy (FSE), stress (PSS), autonomous motivation (TSRQ) and QoL (KSQ). Any negative effect of SPARC on patients QOL will be recorded as part of the secondary outcomes.

**Procedures:** Consent will be obtained either on paper or eConsent will be obtained using Redcap. Following informed consent, SPs will be randomly assigned to SPARC or enhanced standard of care (SC) control group using the randomization module of the web-based REDCap study database. Standard of care includes education on stress and sarcoidosis fatigue, as well as recommending referral to pulmonary rehabilitation. Those in SPARC group will have SPARC app downloaded on their phone by the research coordinator. Use of the App will be reviewed and the subject will demonstrate ability to navigate the app, use components without assistance prior to leaving clinic. The research coordinator will assist in ensuring the SP have performed the first SPARC BAM session properly and completed the appropriate questionnaires prior to leaving the clinic.

A review of concomitant medications will be collected at the screening visit and reviewed at all study visits for changes. There are no patient-safety related adverse events possible, but any negative effect of SPARC on patients QOL will be recorded as part of the secondary outcomes. All SPs will return to clinic at weeks 4, 12 and 24 for routine clinical care. During those visits, questionnaires will be given, according to the Schedule of Assessments (Table 1-2). Questionnaires will be given orally or read on their own, based on their preference.

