## **12 RISKS TO THE SUBJECTS**

### **12.1 Human Subjects Involved and Characteristics**

Admission into the study is open to men and women 18 years of age or older, and to all racial and ethnic groups. A total of 50 subjects will be enrolled. The primary source of recruitment will be through screening of sarcoidosis patients seen in the Sarcoidosis Clinic at the Susan Pearlstine Sarcoidosis Center of Excellence at MUSC. We will also advertise the study through MUSC's sarcoidosis website, the Foundation for Sarcoidosis Research's website, and word of mouth among subjects.

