### **12.4 ADEQUACY OF PROTECTION AGAINST RISKS**

#### **12.4.1 Recruitment and Informed Consent**

## SPARC

Subjects will primarily be recruited from the Sarcoidosis Clinic at MUSC. Medical records will not be routinely reviewed to identify potential subjects, except when providers suggest evaluating specific individuals who they feel may be candidates. All patients attending the Medical University of South Carolina Pulmonary Clinics who may be eligible will be recruited for participation in the study. In addition, a chart review will be conducted by the research coordinator and/or the PI for research purposes for all patients seen at MUSC who may meet study eligibility. The initial approach to the prospect to ascertain the patient's level of interest will be done by their treating physician (i.e., no cold calling). Interested patients will be offered participation in the study during a routine or previously scheduled clinic visit; or contact by a study team member. The study will also be advertised using flyers in waiting areas, sarcoidosis patient support group meetings (hosted at MUSC quarterly), and the MUSC website. All other patients (outside of MUSC) will be contacted through their providers to be informed of the study if the provider feels it is appropriate.

Eligibility for the study of screened patients will be tracked, and we will keep a record of number of potential participants screened, including reasons for exclusion/refusal. For each potential participant, we will review all eligibility criteria rather than stopping at the first reason for exclusion encountered. Those deemed eligible based on criteria will proceed to consent.

Consent will be obtained by the study PI, a Co-I, or other qualified study staff. The informed consent process will include a detailed description of study procedures and the SPARC app. Subjects will be clearly informed of their right to withdraw from the study at any time without consequences. The informed consent form will be written at an eighth grade reading level and will be explained in easy-to-understand language. Subjects will be instructed and encouraged to read the form carefully prior to signing it. The subject placing their signature on the informed consent form in addition to the signature of the individual obtaining consent will document confirmation of consent.

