### 14.2 Data Analysis

Descriptive statistics will be calculated for all measures and variables. We will use 95% CIs for proportions to estimate dichotomous feasibility outcomes (e.g., proportion who agree to participate out of total approached, proportion adherent to SPARC protocol, and proportion who drop out). Frequency distributions will be developed describing participants' reasons for non-adherence and discontinuation of SPARC app use and problems/issues encountered with the app. For continuous usability measures (e.g., frequency, duration of use; surveys-SUS,TSUQ,uMARS), frequency distributions & median and mean responses (with 95% CIs) will be obtained. Mean change and difference in change between the groups from pre-to-post intervention along with their 95% CIs will be reported for all continuous secondary (impact) outcomes (change in PSS-10, FAS, QoL, FSE & TSRQ scores). Preliminary analyses will

SPARC

examine a) underlying distributional properties of all outcome variables b) patterns of missing data, and c) patterns of attrition. Linear mixed-models for repeated measures will be used for the continuous impact measures to obtain estimates of intra-cluster correlation (ICC) & variance estimates along with covariance structure of longitudinal scores used as critical information for sample size calculation of a future efficacy RCT. Based upon Shieh's work, we have inadequate sample size & lack of adequate power to run formal moderator analyses. These analyses will be run in the future appropriately powered RCT to examine impact of socio-demographic variables as potential adherence barriers, as well as potential moderating effects of disease severity (i.e. lung function), fatigue-inducing medications and SPARC meditation adherence on secondary outcomes

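### Section 7 stratifies randomisation by healthcare provider, but the allocation step in 9.1.3 names no strata and the 14.2 between-arm analysis has no provider term

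*Combined protocol and SAP*

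**What the plan says.** Section 7, Specific Aim 1, sets the design: "They will be randomly assigned to SPARC or an enhanced attention control group stratified by healthcare provider". This is the only mention of a stratification factor. The protocol does not define healthcare provider or say how many there are.

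Section 9.1.3 (Procedures) describes the allocation: "SPs will be randomly assigned to SPARC or enhanced standard of care (SC) control group using the randomization module of the web-based REDCap study database". It states no stratum, allocation ratio or block scheme. The equal split appears only in Section 14.1, as 25 per group.

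Section 14.2 reports mean change per group and the difference in change between groups, each with a 95% confidence interval. It then adds: "Linear mixed-models for repeated measures will be used for the continuous impact measures". These models are to supply an intra-cluster correlation, variances and a covariance structure for sizing a later efficacy trial. No provider term is listed.

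Recruitment source, which bears on what a provider stratum could be, is described in three ways:
- Section 9.1.2: "All SPs will be recruited at MUSC's Sarcoidosis Clinic".
- Section 12.1: "The primary source of recruitment will be through screening of sarcoidosis patients seen in the Sarcoidosis Clinic", with website advertising and word of mouth added.
- Section 12.4.1: "All other patients (outside of MUSC) will be contacted through their providers to be informed of the study if the provider feels it is appropriate".

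**The concern.** A stratification factor has to appear in three places: the design statement, the allocation list and the analysis. Here it appears only in the design statement. Someone building the REDCap list from 9.1.3 would leave it unstratified. Someone working from Section 7 would have to guess the strata.

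Two outputs are at stake. The first is the set of between-arm intervals for change in the secondary outcomes. If arms are balanced within provider but the analysis ignores provider, any provider differences in change stay in the residual. The interval is then wider than the design warrants. The second is the set of variance and correlation estimates for the future trial. A provider difference in level that is constant over time cancels out of a change score, but in a repeated-measures model without a provider term it is absorbed into the between-patient variance and so into the intra-cluster correlation.

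**Working it through.** **1. Inputs.** From Section 14.1: 50 patients, 25 per group, 95% confidence, SD 5.0 to 6.7 for between-group differences in change, and SD 3.7 to 6.1 for within-group change. The protocol gives no provider effect, number of providers, stratum sizes or block size. Any value used for these below is an assumption.

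**2. Reproducing the plan's own figures.**
- Between-group half-width = 1.96 × SD × √(1/n1 + 1/n2). With 25:25, √(1/25 + 1/25) = 0.2828. This gives 1.96 × 5.0 × 0.2828 = 2.77 and 1.96 × 6.7 × 0.2828 = 3.71. The plan states 2.8 to 3.7.
- Within-group half-width = 1.96 × SD / √n. With n = 25 this gives 1.45 to 2.39. The plan's upper end is 2.4; its lower end is misprinted but evidently means 1.5.
- Proportions: 1.96 × √(p(1−p)/50) gives 0.083 at p = 0.10 and 0.127 at p = 0.30. The plan states 0.08 to 0.13. These use all 50 patients and do not depend on the split.

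The between-group figures contain no adjustment for provider.

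**3. What leaving provider out costs.** Let R² be the share of within-arm variance in change that provider explains. With provider balanced across arms, the unadjusted half-width exceeds the adjusted one by a factor of about 1/√(1 − R²). The documents do not give R². As an assumed range only:
- R² = 0: factor 1, no loss.
- R² = 0.05: 1/√0.95 = 1.026.
- R² = 0.10: 1/√0.90 = 1.054. If the Section 14.1 SDs include provider variation, 2.77 to 3.71 would become 2.63 to 3.52 after adjustment.

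**4. What putting provider in costs.** Two or three strata use one or two degrees of freedom. For a comparison of two means in 50 patients, the t multiplier moves from 2.011 (48 df) to at most 2.013 (46 df), about 0.1%.

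**5. What unequal arms would cost.** The same formulas with other splits give:

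| Split | Between-group half-width | Change | Within-group, smaller arm | Change |
|---|---|---|---|---|
| 25:25 | 2.77 to 3.71 | – | 1.45 to 2.39 | – |
| 22:28 | 2.79 to 3.74 | +0.7% | 1.55 to 2.55 | +7% |
| 20:30 | 2.83 to 3.79 | +2.1% | 1.62 to 2.67 | +12% |

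Simulated permuted blocks of 2, 4 or 6 within assumed strata show when such splits occur. With three clinic strata of 20, 18 and 12, the 95th percentile of the arm-size difference is 0 to 2 patients. With three clinic strata plus 10 single-patient strata it is 6 to 8. With 20 single-patient strata it is 10, that is 20:30.

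**The case against.** Several counter-arguments have force.

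- **Silence is not contradiction.** Nothing in 9.1.3 rules out stratification, and an unstated block rule may still exist in the REDCap set-up. Section 14.2 is an outline that lists no covariates at all and does not say what the cluster in its intra-cluster correlation is. This stands as far as it goes: the plan does not exclude provider. It also does not say that provider is included, and a stratification factor should not be left to inference.
- **The loss is conditional and unquantified.** This also stands. If provider does not affect outcome, the loss is nil.
- **Dropping the factor would cure the inconsistency equally well.** True for the text. It would give up a design feature that Section 7 has chosen and that costs almost nothing to carry through.

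A reader might go further and infer from 12.1 and 12.4.1 that each outside provider forms a stratum of one patient, so that the 25:25 split is lost. With assumed clinic strata of 18 and 17, 15 outside patients each with a different provider, and blocks of 4, a 28:22 or worse split does occur in about 24% of simulated allocations. The documents do not establish that scenario. It requires provider to mean the outside referring clinician. The trial has one site, 9.1.2 places all recruitment at its clinic, all patients attend that clinic at weeks 4, 12 and 24 (9.1.3), and travel of more than two hours is an exclusion (10.2). A few strata of treating clinic providers are at least as likely. Sections 12.1 and 12.4.1 say how people hear of the study, not which stratum they would enter. Even if the scenario held, a 22:28 split costs the between-group interval 0.7%. The plan already accepts up to 20% drop-out (14.3), which leaves 20 per arm and costs about 12%.

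**Conclusion.** The point holds as a gap between design, procedure and analysis. Provider is declared as the stratification factor, is undefined, and is absent from both the allocation step and the between-arm model. The consequence is intervals that are wider than needed, and planning variances larger than they need be, if and only if provider explains outcome variation. The documents do not allow that size to be fixed; the percentages under an assumed R² are illustrations.

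The gap does not undermine the stated precision of this feasibility trial. Single-patient strata are possible but not shown, and the proportion figures are unaffected by the split. The conflict over recruitment source is a matter for clarification, relevant here because it decides who can belong to which stratum.

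**What to change.** 1. In Section 7, define healthcare provider and list the strata. One workable form is the treating MUSC sarcoidosis provider or providers, with every patient not followed by one of them in a single pooled stratum, so that outside patients do not each form their own.
2. In Section 9.1.3, enter the same strata in the REDCap allocation step, and state the ratio and that a block scheme is used.
3. In Section 14.2, include the stratum as a fixed effect in the mixed model and in the estimates of between-group difference in change. Say what the cluster in the intra-cluster correlation is.
4. Reconcile Sections 9.1.2, 12.1 and 12.4.1 on where patients may come from.

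The cost is protocol wording, set-up of the allocation list and one model term. The downsides are one or two degrees of freedom and the loss of individual balance across outside providers within the pooled stratum. If the sponsor no longer wants the factor, deleting it from Section 7 also restores consistency, but gives up any gain in precision from it.
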